7.2. Data Entry and Storage

Data will be entered electronically into Microsoft Excel spreadsheet, which is password protected, with only the Principal Investigators and Co-Investigators having access to the data.

8. SAMPLE SIZE AND STATISTICAL METHODS

8.1. Determination of Sample Size

There is no sample size calculation for this pilot study. The Weight Management Clinic receives new referral to WMC of 20 new patients per month with approximately 20% of the new referrals being adolescents (10). Using a conservative estimate of 50% uptake rate, we will be able to get 2 patients per month over 20 months to get 45 adolescents enrolled into Kurbo program.

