2. HYPOTHESIS AND OBJECTIVES

Primary objective will be to examine the proportion of patients triaged to the low risk WMC clinics after brief intervention by a nurse coordination and completion of 4 sessions of Kurbo Program over a 12 month recruitment period.

Secondary objectives:

1. To examine the effect of the waitlist intervention and WMC intervention on mean BMI z-score change at 3 months and 6 months.
2. To examine the feasibility of using Kurbo program as a waitlist intervention for the target population as measured by quantifying the percentage of patients offered the program who agreed to enrol.
3. To examine program fidelity as measured by the percentage of patients who complete each of the 12 sessions of online coaching by Kurbo coaches
4. To examine changes in treatment outcomes as a function of program fidelity as measured by those who complete more online coaching show greater improvements in BMI z-score
5. To examine other factors that predict poor response (parental BMI, quality of life, disordered eating and physical activity measurement) in high risk WMC
6. To examine the effects of waitlist intervention on lifestyle changes (nutrition and physical activity), quality of life and disordered eating at 3 and 6 months.
7. To examine the rate of attrition from WMC after implementation of the waitlist intervention and new model of care in WMC.
8. Examine changes in branched chain amino acid(BCAA), aromatic amino acid (AAA) and long chain acylcarnitines, insulin and second hour glucose results and fasting lipids at baseline and at month 6.

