4. STUDY POPULATION

4.1. List the number and nature of subjects to be enrolled.

45 adolescents, aged 10-17 years old, will be recruited in KKH

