5. STUDY DESIGN AND PROCEDURES/METHODOLOGY

Children aged 10-17 years old with BMI percentile of above 90th percentile, who are referred to the WMC, will receive a brief intervention by the WMC nurse coordinator followed by introduction to Kurbo program for more detailed dietary and physical activity recommendations and implementation of behavioural changes. The patient's progress will be reviewed by the nurse clinician at one month post intervention to determine whether the BMI percentile has shown a reduction through the Kurbo Program. Patients that declined Kurbo intervention, has a BMI of more than 99th percentile or continue to have increase in their BMI percentile in Kurbo program, will be offered the high risk weight management clinic appointment for a more detailed multidisciplinary evaluation for targeted intervention. Patients that are able to engage with Kurbo intervention and showed a decrease in BMI percentile over 4 sessions of Kurbo will be offered the low risk weight management clinic.

The following section illustrates how and when the outcomes will be measured. Figure 1 depicts the flow diagram for an adolescent at the point of referral to the WMC.

Figure 1: Flow diagram of the intervention at the point of referral to WMC

Study visits and procedures

The expected duration of study involvement for each participant will be 6 months with 5 in-person visits with the study team. Table 1 depicts the study visits and measurements for each visit.

Table 1: Study visits and measurements

	Baseline	Visit 1	Visit 2	Visit 3	Visit 4	Visit 5
Parental demographics and parental BMI	x					
Anthropometry (weight, height, waist circumference, blood pressure and body fat composition)	x		x	x		x
Peds QL questionnaire	x			x		x
Three day food diary	x			x		x
Eating Pattern Inventory	x			x		x
Evaluation questionnaire				x		
Accelerometry	x			x	x	
Fasting insulin, lipids, oral glucose tolerance test		x			x	
Plasma amino acid, long chain acylcarnitine levels and vitamin D level, calcium, magnesium, phosphate and alkaline phosphatase		x			x	

First contact (Baseline):

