study team members to assess physical activity. If patients do not turn up for the visit, the clinical research coordinator will call the patient to administer the questionnaire and the food diary and obtain a self report height and weight. The clinical research coordinator will attempt up to 3 times to contact the patient. It will be considered a loss of follow up for that visit if patient returns for visit after the window period of 12-23 weeks.

Visit 4: (week 24-36)

Metabolic blood tests (HbA1C, fasting lipid panel, oral glucose tolerance test, fasting insulin level and liver function test) were collected after a minimum 8 hour fasting period together with bloods for AAA, BCAA and long chain acylcarnitines approximately before visit 5 appointment to aid discussion with the doctor during WMC appointment. **Vitamin D level, calcium, magnesium,phosphate and alkaline phosphatase may be performed to assess the bone health of the adolescents.** Blood tests are optional for patients. Accelerometers may also be fitted or returned to study team members to assess physical activity.

Visit 5: (week 24-36)

The follow up will be timed together with the WMC appointment to measure the patient's weight and height, body fat composition, waist circumference and blood pressure as well as administration of the questionnaire. Accelerometers may also be fitted or returned to study team members to assess physical activity. If patients do not turn up for the visit, the clinical research coordinator will call the patient to administer the questionnaire and the food diary and obtain a self report height and weight. The clinical research coordinator will attempt up to 3 times to contact the patient. It will be considered a loss of follow up if patient returns for visit after the window period of 24-36 weeks.

Anthropometric measurement and blood pressure will be measured by trained staff at each clinic visit. The height and weight were measured to the nearest 0.1 cm via a stadiometer (Seca, Model 220; Germany) and 0.1kg via a medical weighing scale (Tanita HD-316, Tanita Corp.; Tokyo, Japan) respectively without shoes and in light clothing. Blood pressure was measured via an electronic sphygmomanometer (Dinamap model 8101, Critikon Inc.; Florida, USA). Waist circumference is measured at the narrowest point between the lower costal (rib) border and the iliac crest using a nonextensible steel tape.

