13. RETENTION OF STUDY DOCUMENTS

Records for all participants, including CRFs, all source documentation (containing evidence to study eligibility, history and physical findings, laboratory data, results of consultations, etc.) as well as IRB records and other regulatory documentation will be retained by the PI in a secure storage facility under key and lock. The records will be accessible for inspection and copying by authorized authorities and will be stored for 6 years after the study is completed.

14. FUNDING and INSURANCE

Grant agency is Paediatrics Academic Clinical Programme under the grant name: Tan Cheng Lim Research and Education Fund Grant Award. The grant has been approved with the budget allocation of \$50,000 over 1.6 years from 01 April 2017 to 30 November 2018.

The participants will be reimbursed SGD50 to compensate the travelling expenses for each visit they attend in the window period.

List of Attachments

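### Recruitment lasts 12 months in the primary objective and 20 months in section 8.1; at the plan's own rate these give about 24 and 40 patients, and neither gives the stated 45

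*Combined protocol and SAP*

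**What the plan says.** Section 2 defines the primary objective as the proportion of patients triaged to the low risk clinic after the nurse's brief intervention and four Kurbo sessions, "over a 12 month recruitment period".

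Section 4.1 gives the number to be enrolled: "45 adolescents, aged 10-17 years old, will be recruited in KKH".

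Section 8.1 states that this pilot has no sample size calculation and offers an accrual estimate instead. It starts from 20 new referrals a month, with "approximately 20% of the new referrals being adolescents". It assumes that half of these will take part, which it regards as cautious, and concludes: "we will be able to get 2 patients per month over 20 months to get 45 adolescents enrolled into Kurbo program".

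No section explains how 12 months relates to 20 months, or how 2 a month for 20 months becomes 45.

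**The concern.** Two current sections give different lengths for the same recruitment period, and one of them is the primary objective. Rounding cannot turn 12 into 20. Separately, the accrual sentence in section 8.1 does not multiply out to its own total.

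The main result of this study is a single descriptive proportion, so its precision depends directly on how many adolescents are recruited. With no formal calculation, the accrual sentence is the only basis the plan offers for 45. Its uptake assumption matters too, because secondary objective 2 sets out to measure the percentage of patients offered Kurbo who agree to enrol. A reader should be able to see what uptake the plan relies on.

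**Working it through.** **Inputs.** From section 8.1: 20 referrals a month, adolescent share about 0.20, uptake 0.50, 20 months, target 45. From section 2: 12 months. From section 4.1: 45.

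**Step 1: the plan's monthly rate.** Referrals × adolescent share × uptake = 20 × 0.20 × 0.50 = 2 a month. This reproduces the stated rate.

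**Step 2: the plan's total.** Rate × months = 2 × 20 = 40. The stated 45 is not reproduced; the gap is 45 − 40 = 5, and 5/45 = 11%.

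**Step 3: the period in the primary objective.** 2 × 12 = 24. The gap is 45 − 24 = 21, and 21/45 = 47%.

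**Step 4: what 45 would require.**

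- At 2 a month: 45/2 = 22.5 months.
- In 20 months: 45/20 = 2.25 a month. With 4 adolescents referred a month, that is 2.25/4 = 56.25% uptake. With uptake kept at 50%, it is an adolescent share of 2.25/(20 × 0.50) = 22.5%.
- In 12 months: 45/12 = 3.75 a month. That is 3.75/4 = 93.75% uptake, or 45 of the 48 adolescents referred. With uptake kept at 50%, it is an adolescent share of 3.75/(20 × 0.50) = 37.5%.

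**Step 5: precision of the primary proportion.** The plan gives no expected value, so I assume a true proportion of 0.5, which gives the widest interval. The approximate 95% half-width is 1.96 × √(0.25/n).

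| n | Source | Half-width |
|---|---|---|
| 24 | 12 months at 2 a month | 1.96 × 0.102 = 20.0 points |
| 40 | 20 months at 2 a month | 1.96 × 0.0791 = 15.5 points |
| 45 | stated number | 1.96 × 0.0745 = 14.6 points |

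The choice between 12 and 20 months moves the half-width by about 4.5 points. The difference between 40 and 45 moves it by about 0.9 points.

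**The case against.** **The inputs are approximate and this is a pilot.** The adolescent share is given as approximate and the uptake is called conservative, so 2 a month is a cautious figure. A share of 22.5% or an uptake of 56% would give 45 in 20 months. This largely disposes of 40 versus 45. It does not help the 12-month figure, which needs about 94% uptake or nearly double the stated adolescent share.

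**Patients lost from the primary analysis.** A reader might infer that the objective drops everyone enrolled in months 13 to 20, which at 2 a month is 16 of 40. The documents do not support this. It requires recruiting for 20 months while counting only the first 12, and no section sets such a cut-off. Section 2 describes the 12 months as the recruitment period. Taking either figure alone, everyone recruited counts.

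**Twelve as the obvious slip.** It is tempting to say so because 20 months sits next to 45 in section 8.1. The funding dates in section 14 point the other way. The grant runs "over 1.6 years from 01 April 2017 to 30 November 2018", which is 9 + 11 = 20 calendar months, and section 5 says "The expected duration of study involvement for each participant will be 6 months". If recruitment began with the grant, 12 + 6 = 18 months would fit and 20 + 6 = 26 would not. The plan does not say when recruitment begins, or that follow-up must end with the grant. The dates therefore neither settle which figure is intended nor show that 20 months is unworkable.

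**Forty-five of what?** Section 4.1 speaks of adolescents recruited and section 8.1 of adolescents enrolled into Kurbo. Section 5 sends those who decline Kurbo to the high risk clinic, so the two counts need not be the same. This stands as a caution: one recruitment period fixes the expected size, but does not by itself say whether decliners belong in the primary denominator.

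**Conclusion.** The point holds as an unreconciled inconsistency with a modest arithmetic slip beside it. The 12 and 20 months conflict, and the documents do not show which is meant. At the stated rate the expected number is about 24 or about 40, and neither is 45. The 20-month gap (11%) is within what approximate inputs could explain; the 12-month gap (47%) is not.

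The consequence is uncertainty about the expected size and precision of the primary proportion, with a half-width anywhere from about 15 to 20 points. That range assumes a true proportion of 50%, the normal approximation, and steady accrual at the plan's own rate. Type I error and power are untouched. The sponsor should correct this because it sits in the primary objective and is cheap to put right; the 40-versus-45 discrepancy alone would be minor.

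**What to change.** Give one recruitment period in section 2 and section 8.1. Then do one of the following:

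- Restate the expected number in sections 4.1 and 8.1 to match the period: about 40 for 20 months, or about 24 for 12 months.
- Keep 45 and state the inputs that give it: about 22.5 months at 2 a month, or 2.25 a month over 20 months through about 56% uptake or an adolescent share of about 22.5%.

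The same edit could say whether 45 counts all recruited adolescents or only those enrolled into Kurbo.

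The change is one of wording. Its price is a smaller stated number (slightly smaller for 20 months, about half for 12), a less conservative accrual assumption, or 2.5 more months of recruitment than section 8.1 plans. The chosen period should also be checked against the grant dates in section 14, as a matter of context only.

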8.2. Statistical and Analytical Plans

Data will be analysed using SAS version 9.3 for Windows (SAS, Inc., Cary, NC USA). BMI will be calculated as kg/m² and BMI-z score calculated using the L, M, S parameters published by the CDC. (34) Baseline demographic, anthropometric measurements, parental BMI, quality of life measurement, disordered eating and physical activity were compared between those in low risk WMC versus those in high risk WMC using the Wilcoxon rank-sum test and the two-sample-t-test for non-normal and normal continuous variables, respectively, and the Fisher's exact test for categorical variables. Changes in cardiometabolic risk factors between first visit and at month 12 will be compared using the paired-sample t-test. Generalized linear mixed model will be carried out on the BMI z-score over multiple visits over 12 month follow up period. The mean value of BMI z-score is considered as a function of time from the baseline. The variance components is used as the covariance structure in generalized linear mixed model. It models a different variance component for each random intercept to allow each child to have his/her own overall level of BMI z-score after taking into account baseline covariate. A time-group interaction will be included to test whether the rate of change of BMI z-score is different between adolescents in low risk and high risk WMC.

There is no reason to assume that this project will lead to an excess of adverse events as the waitlist intervention consists of advice from the nurse and offer of referral to a Kurbo program, neither of which seem likely to create harm. Nonetheless, there are several safety net in place for the waitlist intervention. Firstly, as part of standard Kurbo procedures, any excessive weight loss or weight gain will prompt the Kurbo coaches to inform parents to seek help from their GP and the WMC nurse coordinator will be informed if any concerns arise. Secondly, the WMC nurse coordinator will have administrative rights to Kurbo program and will be able to monitor patient's weight data and communication with Kurbo coaches and will highlight any concerns that arise as a result of intervention. There will also be a feedback form (A month 3 evaluation) administered by the clinical research coordinator on the participants' attitudes to the waitlist intervention and to identify any adverse events at the first WMC visit. As this is a pilot study, there will be no interim analyses.

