1. BACKGROUND AND RATIONALE

Prevalence of overweight and obesity amongst Singaporean adolescents has increased from 11 to 12 per cent in 2014 in school children (1) Current numbers of adolescents who are overweight or obese are predicted increase to 148,000 in year 2025. Adolescents who are overweight or obese have a moderate to substantial risk of remaining so in adulthood and they suffer from a range of immediate and long term medical and psychosocial complications. (2, 3) In addition, obesity-related cardiovascular disease risk markers present in adolescence are predictive of obesity related morbidity present in adulthood. (4). Importantly, obese and overweight adolescents who became normal weight adults, had cardiovascular disease risk markers that were similar to those of persons who had a normal BMI consistently from childhood to adulthood (5) Overweight and obese adolescents aged 12-15 were also found to have a higher chance of having normal Body Mass Index (BMI) at adulthood compared to children and adolescents of other age groups. (5) This further highlights a golden opportunity for intervention in adolescent obesity. Adolescent obesity is also a costly chronic disease and the lifetime direct medical costs is estimated to cost S\$24,000 more per adolescent relative to a normal weight child. (6) Indirect costs of obesity such as carer's loss of productivity and intangible costs such as loss of well-being further add to the burden of adolescent obesity.

The Expert Committee on the Assessment, Prevention and Treatment of Child and Adolescent Overweight and Obesity(7) recommends a staged based approach to the management of adolescents with overweight and obesity from Stage 1-4 with increasing intensity of management in higher stages. Stage 3 is recommended for overweight and obese adolescents that showed poor response to Stage 1 and 2 or for adolescents with BMI of greater than 99th percentile. These adolescents are termed high risk obesity in our WMC program. Stage 3 interventions consist of multidisciplinary visits with frequent (up to weekly) visits for 8 or more weeks.

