The app's data driven platform provides users with feedback via push notifications, text messages and emails. Kurbo utilizes Traffic Light Diet (18) to categorise foods into reds, yellows and greens. The Kurbo program teaches users to gradually reduce their consumption of red(high caloric) food over time instead of focusing on caloric counting which promotes disordered eating behaviours (19). The app is supplemented with weekly live coaching with a Kurbo behavioural coach. Coaches check in with the adolescents for 15 minutes once a week via video, phone or text. Health care professionals, who referred their patients, will also have access to the patient's progress through the Kurbo administrator site. Briefly, Kurbo coaching philosophy is based on a theoretical model of human support called Supportive Accountability (20). Human increases adherence through accountability to a coach who is seen as trustworthy, benevolent, and having expertise. Details about Kurbo coaching philosophy, screening, training and supervision of coaches is as attached in Appendix 1. Terms and conditions about Kurbo program is attached in Appendix 2. The program is licensed from the Stanford Packard Pediatric Weight Control Program and is currently part of the weight management program in Stanford and Florida's Children weight management clinic. There are also ongoing trials in Baystate Pediatric weight Management Program and University of Chicago on the utility of Kurbo Program. Locally, Health Promotion Board had conducted a pilot study using Kurbo Program on 80 overweight and obese children aged 8-17 years old as a school-based initiative. The pilot study showed a low drop-out rate of 19%. 65 families completed the 3 month program with a significant drop in BMI z-score by 0.26. Of this group, 90% of the children either maintained or reduced their weight. Of those who reduced their weight, 58% reduced their BMI by over 3% and 20% reduced their BMI by over 7%. Reduction of BMI \bar{z} -score of more than 0.25 has been found to be clinically significant for reduction of cardiovascular risk factors. (21)

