Several studies in adolescent obesity have consistently identified early treatment engagement as evidenced by attendance and initial weight loss, between 4-10 weeks, to be strongly predictive of long term weight loss (9, 26, 27). Early responders have been reported in studies varying from 60-80% (9, 27). These data support the hypothesis that a large proportion of obese adolescents can be managed in primary care with structured interventions. Identification of early treatment attendance and initial weight loss introduces a second filter to Stage 3 program. A third filter will be the identification of the severely obese adolescents as severely obese adolescents have been found to have higher risks of obesity related co-morbidities (7) with poor response to treatment (28). Early responders, who are not severely obese, can then be channelled to low risk WMC clinics which are made to simulate a primary care provider clinic with only 10-15 minutes consultation time. If the low risk clinics are found to be successful, it has potential to be implemented widely in primary care. To our knowledge, there have been no clinical program that have utilized a waitlist intervention to identify early responders in WMC as a triage approach.

We thus propose a waitlist intervention with two main components of a brief intervention by a nurse coordinator followed by the Kurbo program to identify early responders, who are not severely obese, in our WMC waitlist system. The waitlist intervention is cost effective and makes only very modest demands on the nurse clinician's time and skills, which is a strategy we have chosen deliberately. If successful, it can be implemented widely as a brief opportunistic intervention and increase the degree to which primary care providers (polyclinic nurses and doctors, general practitioners or school health services) engage with adolescent obesity interventions.

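### The between-clinic slope test uses LMS BMI z-scores alone, so the high risk clinic can show a flatter slope at equal percent BMI loss if L is negative and the heaviest children are concentrated there

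*Combined protocol and SAP*

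**What the plan says.** Section 8.2 fixes the outcome scale as "BMI-z score calculated using the L, M, S parameters published by the CDC". It fits a mixed model to the repeated z-scores and includes a time-by-group interaction "to test whether the rate of change of BMI z-score is different between adolescents in low risk and high risk WMC". On the covariance it says "The variance components is used as the covariance structure in generalized linear mixed model", with a random intercept per child and an unnamed baseline covariate. It gives no values of L, M or S, no other BMI scale and no sensitivity analysis.

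The two groups are not randomised, and weight enters the allocation:

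- Section 1 refers to "adolescents with BMI of greater than 99th percentile. These adolescents are termed high risk obesity in our WMC program" and says "Early responders, who are not severely obese, can then be channelled to low risk WMC clinics".
- Section 5 (opening paragraph) names those to be offered the high risk clinic: "Patients that declined Kurbo intervention, has a BMI of more than 99th percentile or continue to have increase in their BMI percentile".
- Section 5 (Visit 2) sends a child whose BMI percentile fell after four Kurbo sessions to the low risk clinic, with no condition on the 99th percentile. A child with no change, or who did not sign up, goes to the high risk clinic.

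**The concern.** With negative L, the z-score compresses the upper end of the BMI range, so its sensitivity to a given relative BMI change depends on how heavy the child is at the start. Starting weight also helps to decide which clinic the child is in. The interaction could then report a slower improvement in the high risk clinic when both clinics achieve the same percent BMI loss. The random intercept and a baseline main effect do not protect against this: they adjust the level of the z-score, and the compression acts on its slope. At stake is a reader concluding that the high risk programme works less well than it does.

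**Working it through.** The plan states no figure on this point, so there is none to reproduce.

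**Inputs.** From the documents: 45 adolescents (section 4.1), split here as 22 low risk and 23 high risk; entry above the 90th percentile (section 4.3); the 99th percentile boundary (sections 1 and 5). Assumed: L, S, the 22/23 split, a 5% mean BMI fall, an SD of 5% for relative change, and a two-sided 5% test. The boundaries are set at z = 1.282 and z = 2.326, which assumes that the percentiles come from the same CDC reference as the z-scores; the protocol does not say so.

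**Step 1: one child.** The LMS score is z = ((BMI/M)^L - 1)/(L x S), or ln(BMI/M)/S at L = 0. Its sensitivity to relative change is dz/d ln(BMI) = (BMI/M)^L / S = (1 + L x S x z)/S, which falls as z rises if L < 0 and is constant if L = 0. For a 5% BMI fall with age held fixed and L not zero:

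change in z = (1 + L x S x z)(0.95^L - 1)/(L x S).

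Worked case, L = -2, S = 0.13: (0.95^-2 - 1)/(-0.26) = 0.1080/(-0.26) = -0.4155. At z = 1.645 the multiplier is 1 - 0.26 x 1.645 = 0.572, giving -0.238. At z = 2.6 it is 1 - 0.26 x 2.6 = 0.324, giving -0.135. The ratio is 0.57.

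| L (S = 0.13) | Change at z = 1.645 | Change at z = 2.6 | Ratio |
|---|---|---|---|
| 0 | -0.395 | -0.395 | 1.00 |
| -1 | -0.318 | -0.268 | 0.84 |
| -2 | -0.238 | -0.135 | 0.57 |
| -2.5 | -0.196 | -0.065 | 0.33 |

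Over S from 0.10 to 0.15 and L from -1 to -2.5 the ratio runs from 0.89 to 0.07.

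**Step 2: the two clinics.** A contrast between two children is not a contrast between clinics, because the high risk clinic also takes decliners and non-responders at any BMI above the 90th percentile. So 22 against 23 children were simulated with the same distribution of relative BMI change. Starting z was uniform from 1.282 to 2.326 in the low risk clinic. A given share of the high risk clinic lay between 2.326 and 2.75, and the rest matched the low risk clinic. A Welch test on z change stood in for the interaction. Entries are the mean difference in z change (high minus low), with the rejection rate in brackets; S = 0.13.

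| L | 25% above 99th | 50% | 100% |
|---|---|---|---|
| -1 | +0.008 (5%) | +0.020 (6%) | +0.041 (7%) |
| -2 | +0.023 (6%) | +0.044 (9%) | +0.086 (25%) |
| -2.5 | +0.030 (7%) | +0.058 (15%) | +0.109 (61%) |

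With no high risk child above the 99th percentile, or with zero mean BMI change, the difference is at most 0.008 and rejection is about 5%. Testing the change in ln(BMI) in the same setting gives about 5% throughout, as it must when relative changes are equal.

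Section 1 treats a z reduction of more than 0.25 as clinically significant. The artefact for L = -2 to -2.5 with half to all of the clinic above the 99th percentile is 0.044/0.25 = 18% to 0.109/0.25 = 44% of that.

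**Step 3: which companion scale.** A 5% fall changes BMI as a percent of M by 5 x (BMI/M) points. At L = -2, S = 0.13, BMI/M is 0.572^(-1/2) = 1.322 at z = 1.645 and 0.324^(-1/2) = 1.757 at z = 2.6. The changes are 5 x 1.322 = 6.6 and 5 x 1.757 = 8.8 points. Percent of M therefore errs the other way and over-weights heavier children. On ln(BMI/M) the change is ln(0.95) = -0.051 at any starting BMI.

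**The case against.** The strongest reply is that this matters little here. The primary objective is the proportion triaged to the low risk clinic, and no objective in section 2 is a between-clinic slope comparison. Membership of the clinics depends largely on early BMI percentile change, so their slopes differ by construction on any BMI scale, and a companion model does not make the interaction a fair comparison of clinics. This stands, and it limits the point to a minor one. It does not remove it: section 8.2 still plans the test, and the scale artefact is a separate source of difference that can be taken out.

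A second reply is that the z-score is the natural scale, since section 1 gives the school pilot's result as a z-score drop of 0.26 and the clinical threshold as 0.25 z. That is a good reason to keep it. The same paragraph also reports relative change ("58% reduced their BMI by over 3% and 20% reduced their BMI by over 7" per cent), so a relative scale is not foreign to the protocol.

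A reader might also infer from the opening of section 5 that every child above the 99th percentile is in the high risk clinic. The documents do not support that. The wording there is an offer, and the Visit 2 rule puts any child with a reduced percentile in the low risk clinic whatever the starting BMI. Under that rule the concentration of heavy children, and so the artefact, would be smaller.

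**Conclusion.** The point holds conditionally and is minor. The high risk clinic can show a flatter z-score slope at equal percent BMI loss if three things are true: L is negative at these ages, mean BMI changes, and heavier children are concentrated in that clinic. None of these is settled by the documents. The effect is absent at L = 0. It is small at L = -1 or with a quarter of the clinic above the 99th percentile (at most 0.041 z, 5 to 7% rejection). It is material at L = -2 to -2.5 with most or all of the clinic above it (up to 0.109 z, 25 to 61% rejection with all). These figures rest on the assumed S, the assumed SD of relative change and a simple test in place of the mixed model.

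It would be tempting to say that the planned slope comparison is distorted outright. The documents do not support that, because they give neither L nor the share of very heavy children, and their allocation rules disagree.

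**What to change.** 1. Keep BMI z-score as planned. Pre-specify the same mixed model, with the same interaction, on ln(BMI/M) using M from the same CDC table; percent BMI change is an acceptable alternative. ln(BMI/M) suits the planned repeated-measures model and allows for the change in the median with age. Do not use percent of M as the companion.
2. State that a slope difference seen only on the z scale will not be attributed to the clinic.
3. Reconcile the opening of section 5 and section 1 with the Visit 2 rule on children above the 99th percentile, and say which reference the percentiles use. Report the number in each clinic above the 99th percentile at baseline.
4. State that the clinics are partly defined by early BMI percentile change, so a slope difference is built in on any BMI scale and the companion analysis removes only the scale artefact.

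The cost is one extra model and a few sentences; no new data are needed.
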